Author details {5a}	1. Department of Medicine, David Geffen School of Medicine at UCLA, Los Angeles, CA/United States of America 2. Department of Medicine, AIDS Healthcare Foundation, Los Angeles, CA/United States of America 3. Public Health Division, AIDS Healthcare Foundation, Los Angeles, CA/ United States of America
Name and contact information for the trial sponsor {5b}	AIDS Healthcare Foundation

Role of sponsor {5c}

The sponsor played no part in study design; and will play no part in the collection, management, analysis, and interpretation of data; writing of the report; and the decision to submit the report for publication.

39 **Introduction**

40 **Background and rationale {6a}**

41 Syphilis rates have been increasing both in the US and internationally, with incidence higher among
42 men-who-have-sex-with-men and people living with human immunodeficiency virus (HIV)
43 infection (2-4). Currently, benzathine penicillin is the recommended treatment for syphilis in all
44 patients, including those living with HIV infection. Doxycycline and tetracycline are available
45 alternative treatments for non-pregnant patients who are allergic to penicillin (5-8). Injectable daily
46 ceftriaxone is another alternative treatment that may be considered and is safe in pregnancy, as a
47 recent review from our team showed (9).

48 Existing alternative treatment recommendations are based on clinical experience, a limited number
49 of small clinical trials, and case series (5-7, 10). However, each regimen poses clinical challenges.
50 Doxycycline/tetracycline require 14 days of treatment by mouth, with tetracycline requiring four
51 daily doses. Ceftriaxone is administered intramuscularly, just like penicillin, but it requires daily
52 injections for 10-14 days, making adherence potentially problematic. In pregnancy, only benzathine
53 penicillin is recommended due to potential toxic effects of the alternatives or due to insufficient
54 efficacy data (WHO). Shortages of benzathine penicillin worldwide have led to the use of unproven
55 non-penicillin alternatives (10-12).

56 Considering the high cost and time required for developing and approving new antibiotics that can
57 treat syphilis in patients with and without HIV infection, a new approach for identifying new, safe,
58 and efficacious antibiotic treatments for syphilis is necessary. Previously Food and Drug
59 Administration (FDA)-approved antibiotics, that are safe and efficacious in other infections and have
60 a favorable pharmacologic profile suggesting activity against *Treponema pallidum*, may be effective
61 alternatives for treating syphilis.

62 Cefixime is an FDA-approved orally administered third-generation cephalosporin with spectrum of
63 activity and pharmacokinetic profile similar to that of ceftriaxone, a drug which has been used for the

64 treatment for syphilis (13). Cefixime is clinically used for uncomplicated urinary tract infections,
65 upper respiratory tract bacterial infections and in the treatment of uncomplicated *Neisseria*
66 *gonorrhoeae* genital infection (14). To our knowledge, it has never been studied as a treatment for
67 early syphilis.

68 Cefixime has a well-studied pharmacokinetic profile (14-19). Unlike other alternatives for syphilis,
69 adverse event profiles are favorable with cefixime in non-pregnant as well as pregnant patients (20,
70 21) . Nearly 40-50% of the dose is absorbed when it is given orally, whether administered with or
71 without food. Peak concentrations occur between 2 and 6 hours following oral administration of a
72 single 400mg tablet. A single 400mg tablet produces an average peak concentration of approximately
73 3.7µg/mL (range 1.3-7.7µg/mL). Typical blood levels of cefixime after a single dose of cefixime 400
74 mg by mouth are 4.84 µg/ml maximum at 4 hours and above 1.0 µg/ml at 12 hours. Serum protein
75 binding is concentration independent with a bound fraction of approximately 65%. Cefixime is
76 moderately distributed into extracellular water/tissue pools. Its half-life averages to 3-4 hours but
77 may range up to 9 hours in healthy volunteers. Approximately 50% of the absorbed dose is excreted
78 unmodified in the urine within 24 hours and nearly 10% is excreted in bile (10).

79 We therefore believe that cefixime's pharmacokinetic similarity to ceftriaxone and its safety in the
80 treatment of pregnant women could potentially make it a viable option in the treatment of early
81 syphilis.

82

83 **Objective {7}**

84 The primary objective of our study is to determine the efficacy of cefixime 400mg, taken orally two
85 times a day (BID) for 10 consecutive days. Our hypothesis is that cefixime would be an efficacious
86 treatment for early syphilis.

87

88 **Trial design {8}**

89 This is a randomized, open-label, non-comparative pilot clinical trial. Participants will be randomly
90 assigned (1:1 allocation) to receive either the standard of care benzathine penicillin injection or 10-
91 days of oral cefixime. The study will require 2 years to be completed and each participant will be part
92 of the study for one year.

93

94 **Methods: Participants, interventions and outcomes**

95 **Study setting {9}**

96 The study will take place in 3 primary care HIV healthcare clinics and 1 wellness center of the
97 AIDS Healthcare Foundation in Los Angeles and Oakland, California. Healthcare clinics offer HIV
98 and sexually transmitted infection (STI) primary care services while wellness centers are walk-in
99 comprehensive sexual health clinics that offer HIV/STI screening services, STI treatment and other
100 prevention services.

101

102 **Eligibility criteria {10}**

103 The inclusion criteria are:

- 104 1) Clinically or laboratory confirmed new cases of early syphilis (primary, secondary, early
105 latent syphilis) with a plasma Rapid Plasma Reagin (RPR) $\geq 1:8$
- 106 2) 18 years of age or older, capable of providing informed consent
- 107 3) HIV infected individuals must have CD4 T cell count ≥ 350 cells/mm³ and be virologically
108 suppressed (viral load < 200 copies/mL) during the past 6 months
- 109 4) Able to travel to clinic once a day or be available for phone calls or receive text message for
110 at least 7-10 days

111 The exclusion criteria are:

- 112 1) Allergy to cefixime or penicillin
- 113 2) Pregnancy or a positive pregnancy test

- 114 3) Serofast RPR titer (prior titer $\geq 1:8$ without history of 4-fold titer decline)
- 115 4) Recent (within the past 7 days) or concomitant antimicrobial therapy with activity against
- 116 syphilis, namely azithromycin, doxycycline, ceftriaxone or other beta lactam antibiotics (e.g.
- 117 amoxicillin)
- 118 5) A medical condition or other factor that might affect their ability to follow the protocol

119

120 **Who will take informed consent? {26a}**

121 Patients must provide written, informed consent before any study procedures occur (randomization,

122 blood sample collection, treatment). Consent will be obtained by a study team member in a private

123 examination room.

124

125 **Additional consent provisions for collection and use of participant data and biological**

126 **specimens {26b}**

127 Patients will also sign a Health Insurance Portability and Accountability Act (HIPAA) release form

128 allowing access to clinical and laboratory data, including their HIV test results.

129

130 **Interventions**

131 **Explanation for the choice of comparators {6b}**

132 This is a pilot, non-comparative clinical trial designed to collect preliminary efficacy data. It

133 includes an “experimental arm” of participants receiving cefixime and a contemporaneous “control

134 arm” of participants receiving benzathine penicillin. The study was not designed to be adequately

135 powered to show a statistically significant difference in the efficacy between the penicillin and

136 cefixime arms.

137

138 **Intervention description {11a}**

139 Eligible participants who provide their consent are randomized to the two arms of the study.
140 Initially, the study team collects demographic (age, gender, race, ethnicity, contact, sexual
141 orientation) and clinical information (most recent RPR titer, CD4 T cell count, HIV viral load). A
142 venipuncture blood sample is collected by trained clinic staff and it is sent to the laboratory for
143 testing. Testing is conducted on serum using the Arlington scientific RPR test kit (Arlington,
144 Virginia) (22). Participants are randomly assigned to the two treatment groups. Participants
145 assigned to the penicillin arm will receive 1 dose of 2.4M IU benzathine penicillin G on the day of
146 enrollment. Participants who are assigned to the cefixime arm will be given 20 capsules of oral
147 cefixime 400mg on the day of enrollment to take for the following 10 days. Study staff observed
148 receipt of the first dose. Subjects in the cefixime arm will then be asked to return for a clinical
149 assessment or have a phone call assessment with the study team member 2 weeks following
150 enrolment.

151 Study staff will follow up with all participants at 3, 6, and 12 months. In each follow up,
152 participants are asked questions regarding symptoms, antibiotic use in the past 3 months and
153 number of sex partners with whom they had condom-less sex in the past 3 months. A new
154 venipuncture blood sample is also collected for RPR testing

155
156 **Criteria for discontinuing or modifying allocated interventions {11b}**

157 Participants may request to leave the study or they may be withdrawn due to study-related adverse
158 events. If a subject is discontinued from study participation due to an adverse event, they will be
159 evaluated by the study clinicians for the need of additional treatment for syphilis. Safety data will
160 be collected on any subject who is withdrawn from the study.

161 Participants in both study groups may receive additional treatment with penicillin, if they show no
162 response to treatment (stable or absence of 4-fold decline at 6 months).

163

164 **Strategies to improve adherence to interventions {11c}**

165 To ensure retention of participants, follow-up visits will be scheduled to coincide with routine clinic
166 appointments for HIV care or preventive sexual health appointments, which occur every three
167 months. In addition, study staff will contact participants, either over the phone or via text message,
168 before their scheduled follow-up appointment. Finally, participants will receive reimbursement for
169 their time and transportation in the form of a gift card.

170

171 **Relevant concomitant care permitted or prohibited during the trial {11d}**

172 Usual HIV care and treatment for the participant will continue throughout the trial. Concomitant
173 antibiotic use during the participation in the study duration of the trial will be recorded.

174

175 **Provisions for post-trial care {30}**

176 Once participants complete the study, they will be able to continue receiving clinical care from the
177 clinics. Participants study records will be reviewed and if necessary, additional treatment for
178 syphilis will be administered according to the standard of care protocol.

179

180 **Outcomes {12}**

181 The primary outcome is the successful treatment of early syphilis by the 3-, or 6-month follow-up.
182 The participants' RPR titer will be used as the primary measure of outcome. Successful treatment is
183 defined as an equal or greater than 4-fold RPR titer decrease, from baseline to 3 or 6 months after
184 treatment.

[figure not shown]
185

186 **Participant timeline {13}**

187 Participants will be part of the study for 12 months. Study evaluations will occur at 3, 6- and 12-
188 months post-treatment. See Figure 1 for the participant timeline for the trial.

189

190 **Figure 1: Participant Enrollment and Follow-Up Schedule**

191

192

193 **Sample size {14}**

194 The primary analysis will compute the proportion of subjects with a 4-fold decrease (from study
195 entry RPR) in RPR titer from baseline at 6 months in the per protocol analysis population. If we
196 assume a sample size of 40 and the proportion of subjects with a 4-fold decrease in RPR from
197 baseline at 6 months to be 0.9 (90%), we would have a 95% confidence interval of (0.76, 0.97). To
198 calculate the number of subjects required to enroll to reach 40 evaluable subjects in the PP analysis
199 population, the assumptions that 20% of subjects will be excluded from the PP analysis population
200 (due to loss to follow-up or non-compliance with study medication schedule). Under that
201 assumption, enrolling 50 subjects will provide 40 subjects in the PP analysis population.

202

203 **Recruitment {15}**

204 Participant recruitment will occur in 4 AIDS Healthcare Foundation (AHF) Clinics based in Los
205 Angeles, California and Oakland, California. Study clinicians will review the medical and
206 laboratory records of syphilis cases returning for treatment before the scheduled clinical visit and if
207 the participant fulfils the eligibility criteria, they will be invited to participate in the study.

208

209 **Assignment of interventions: randomization**

210 **Sequence generation {16a}**

211 After consent, participants are randomly assigned to the study arms with a 1:1 allocation. We will
212 use a simple randomization method with a shuffled deck of sealed envelopes that contain a card
213 with the assigned treatment. The cards are created before the enrollment period and distributed to
214 each of the study sites. No other factors will be taken into consideration for randomization.

215 **Concealment mechanism {16b}**

216 The envelopes containing the randomization cards are sealed, thus the team member conducting
217 enrollment does not know the content of the envelope.

218 **Implementation {16c}**

219 The study staff will ask the participant to select a sealed envelope from the shuffled deck. After
220 selecting the envelope, the participant will reveal the treatment to themselves and the study staff.

221

222 **Assignment of interventions: Blinding**

223 **Who will be blinded {17a}**

224 This is an open label clinical trial, while neither the participants nor the study staff will be blinded
225 to the assigned treatment, staff performing statistical analyses will be masked to treatment
226 assignment.

227 **Procedure for unblinding if needed {17b}**

228 Not applicable.

229 **Data collection and management**

230 **Plans for assessment and collection of outcomes {18a}**

231 A venipuncture blood sample will be collected at 3, 6, and 12 month visits and it will be tested for
232 RPR titer.. Study data collected on baseline include basic demographic information, sexual history,
233 laboratory tests (CD4 count, viral load, RPR titer). On each follow up visit, sexual history,
234 antibiotic use, symptoms and the RPR titer will be collected. Data will be collected on paper data
235 collection forms and will be entered into Research Electronic Data Capture (REDCap) (23, 24).

236 **Plans to promote participant retention and complete follow-up {18b}**

237 Study follow-up visits are scheduled to coincide with routine clinic appointments within AHF.
238 Study staff will send participants a 1 month, 2 week, and 1 day notification prior to their follow-up
239 appointment.

240 **Data management {19}**

241 Participant data will be collected on paper data collection forms and entered into RedCap. Data that
242 will be entered into RedCap include participant information (name, date of birth, medical record
243 number, contact information) and laboratory results.

244 **Confidentiality {27}**

245 Redcap servers are encrypted, HIPAA-compliant, password protected and accessible only by
246 designated study members. Hard copy data collection forms will be stored into a locked cabinet
247 with limited access only to designated members.

248

249 **Plans for collection, laboratory evaluation and storage of biological specimens for genetic or** 250 **molecular analysis in this trial/future use {33}**

251 There are no plans in this trial to evaluate or store biological specimen for genetic or molecular
252 analysis for future use.

253

254 **Statistical methods**

255 **Statistical methods for primary and secondary outcomes {20a}**

256 The primary analysis for the main outcome will be conducted on the “Per Protocol” (PP)
257 population. This will include participants who satisfy the inclusion and exclusion criteria,
258 completed treatment (i.e. received the penicillin injection or received all of the cefixime pills),
259 report no adverse events, returned for follow-up visits (3 and/or 6 months) and have an evaluable
260 RPR result.

261 For each treatment group, we will calculate the proportion of PP participants who achieved a 4-fold
262 RPR titer decrease at 3, or 6-months post-treatment and the exact binomial 95% confidence
263 interval.

264

265 **Interim analyses {21b}**

266 A summary of the enrollment progress, treatment success proportions, adverse events and protocol
267 deviations will be provided to the Data Safety Monitoring Board members.

268

269 **Plans to give access to the full protocol, participant level-data and statistical code {31c}**

270 The protocol of the study is publicly available on [clinicaltrials.gov](https://clinicaltrials.gov/ct2/show/study/NCT03660488) (NCT03660488). Deidentified
271 data will be available upon request to the study Primary Investigator.

272

273 **Oversight and monitoring**

274 **Composition of the coordinating center and trial steering committee {5d}**

275 The immediate study research team based in the University of California of Los Angeles meet on a
276 weekly basis. The immediate team is joined by a wider team of AHF study clinicians, based in
277 study clinics, who also meet on a weekly basis.

278

279 **Composition of the data monitoring committee, its role and reporting structure {21a}**

280 The Data and Safety Monitoring Board (DSMB) will be composed of a physician, biostatistician,
281 regulatory affairs specialist/ethicist and will oversee the study throughout the 2-year study period.
282 They will review study activities every 6 months. The committee will review safety data and
283 clinical efficacy reports and report their decision to the Primary investigator.

284

285 **Adverse event reporting and harms {22}**

286 The study site investigators will report serious adverse events and adverse events to the responsible
287 IRB for that study site in accordance with respective IRB policies and procedures. Follow-up

288 information to a reported adverse event will be submitted to the IRB as soon as the relevant
289 information is available.

290

291 **Frequency and plans for auditing trial conduct {23}**

292 The trial and individual clinic sites will be audited at least once during the duration of the study by
293 the study sponsor (AIDS Healthcare Foundation).

294

295 **Plans for communicating important protocol amendments to relevant parties (e.g. trial 296 participants, ethical committees) {25}**

297 Amendments will be submitted to the IRB according to policies and guidance. Any protocol
298 changes will be promptly communicated to the IRB, the DSMB and the study team.

299

300 **Dissemination plans {31a}**

301 We plan to disseminate study results through peer-reviewed journal publications and conference

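### Only the cefixime arm has a 2-week assessment, so adverse events, and the per-protocol exclusions they trigger, are likely to be picked up unequally between arms

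*Combined protocol and SAP*

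**What the plan says.** Intervention description {11a} has staff observe the first cefixime dose and then sets the early contact for that arm: "receipt of the first dose. Subjects in the cefixime arm will then be asked to return for a clinical" "assessment or have a phone call assessment with the study team member 2 weeks following" enrolment. What is asked at that contact is not stated. No matching contact is described for the penicillin arm, which is treated on the day of enrolment.

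The assessments common to both arms come later: "Study staff will follow up with all participants at 3, 6, and 12 months. In each follow up", "participants are asked questions regarding symptoms, antibiotic use in the past 3 months and" recent condomless partners. No adverse-event question is named there, nor in the collection plan in {18a}.

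Statistical methods {20a} makes the PP population primary. Among its conditions, participants must "report no adverse events, returned for follow-up visits (3 and/or 6 months) and have an evaluable" RPR result. The adverse-event condition has no limit by grade, cause or timing.

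On masking, {17a} says: "This is an open label clinical trial, while neither the participants nor the study staff will be blinded" to treatment; only the statistical staff are masked. Under {21b} and {21a}, adverse-event summaries go to the DSMB, which reviews safety data every 6 months. Adverse event reporting {22} covers onward reporting to the IRBs, not how events are elicited.

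**The concern.** Two provisions interact. One gives the cefixime arm an additional occasion, just after its 10-day course, on which an event can come to light. The other removes from the primary analysis anyone in whom an event has come to light. If both arms had the same true frequency of adverse events, the plan as written could still exclude more cefixime than penicillin participants, because one arm is assessed earlier and once more than the other. Neither participants nor site staff are masked, so nothing in the design counteracts this.

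Two things are at stake. The first is the primary result: the cefixime PP proportion would be computed in a group selected by how closely it was observed, and the penicillin proportion in a group selected differently. The second is the safety record. Even if adverse events played no part in PP membership, the counts by arm reaching the DSMB would come from unequal collection, and an early penicillin event could go unrecorded or depend on recall at month 3.

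**Working it through.** **The plan's own figures.** Sample size {14} assumes 40 evaluable participants and 90% success. The exact (Clopper-Pearson) 95% interval for 36/40 is 0.763 to 0.972, which matches the stated (0.76, 0.97). Enrolment is 40 / (1 − 0.20) = 50, which also matches. The 20% allowance names loss to follow-up and non-compliance; exclusion for adverse events is not listed.

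**Assessments side by side.**

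| Time | Cefixime | Penicillin |
|---|---|---|
| Enrolment | First dose observed | Injection given |
| Week 2 | Clinic or phone assessment | None described |
| About month 2 onward | Appointment reminders {18b} | Appointment reminders {18b} |
| Months 3, 6, 12 | Follow-up assessment | Follow-up assessment |

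**Inputs for the illustration.** The documents give no adverse-event rate and no detection rate, so these are assumptions:

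- True risk of at least one adverse event: 20%, the same in both arms.
- Share detected: 90% with the 2-week contact, 30-50% without it.
- Otherwise evaluable per arm: 20, from 50 enrolled in total, split 1:1, less 20% (25 × 0.8). The plan does not say whether 50 is the total or per arm; if per arm, the figure is 40.

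**Exclusions from the PP set** = otherwise evaluable × true risk × share detected.

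- Cefixime: 20 × 0.20 × 0.90 = 3.6.
- Penicillin: 20 × 0.20 × 0.30 = 1.2, up to 20 × 0.20 × 0.50 = 2.0.
- With 40 per arm: 7.2 versus 2.4 to 4.0.
- With 90% detection in both arms: 3.6 in each, so the imbalance disappears.

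The count is of participants, not events; a second event in the same person excludes nobody further.

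**Effect on the PP proportion.** Let overall success be 0.90, q the fraction excluded for adverse events, and s the success rate among those excluded. PP success = (0.90 − q × s) / (1 − q). Here q = 0.20 × 0.90 = 0.18 for cefixime, and 0.20 × 0.30 = 0.06 to 0.20 × 0.50 = 0.10 for penicillin.

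| s (assumed) | Cefixime, q = 0.18 | Penicillin, q = 0.06 to 0.10 |
|---|---|---|
| 0.70 | 0.774 / 0.82 = 0.944 | 0.858 / 0.94 = 0.913 to 0.83 / 0.90 = 0.922 |
| 0.90 | 0.900 | 0.900 |
| 1.00 | 0.72 / 0.82 = 0.878 | 0.84 / 0.94 = 0.894 to 0.80 / 0.90 = 0.889 |

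True success is 0.90 in both arms on every row. The cefixime figure can move up or down, and it stays put if adverse events are unrelated to response. Under these inputs the spurious gap between arms is about 1 to 3 percentage points. For scale, the exact 95% interval for 18/20 is 0.683 to 0.988.

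**The case against.** The strongest reply is that more frequent detection under cefixime is an inference. The content of the 2-week contact is not specified, and it might be mainly an adherence check, since PP membership also depends on completing the capsules. That stands: a reader might infer that cefixime events will certainly be found more often, and the documents do not go that far. They do call it an assessment, and one held just after a 10-day course is a natural occasion for events to surface, so likely is a fair word.

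A reader might also infer that penicillin participants hear nothing from the study until month 3. That is too strong. Reminders by phone or text start one month before each visit ({11c}, {18b}), so contact begins at about month 2, and a reaction at the injection visit could be seen on the spot. The reminders are appointment notices, however, not assessments. Inclusion criterion 4 requires everyone to be able to attend or be reachable for 7-10 days, but no penicillin contact in that window is described. The participant timeline figure is not available to this review and could show another contact; the text of {13} lists evaluations only at 3, 6 and 12 months.

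The trial is declared non-comparative, with a separate proportion and interval for each arm and no adverse-event outcome. This rules out reading the point as a biased efficacy test. It does not remove the effect on the cefixime proportion itself, and {6b} describes the penicillin group as a contemporaneous control, which invites a side-by-side reading.

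Finally, the exclusions arise from the PP rule, not from the contact schedule. Dropping that condition would end the unequal exclusion, but the unequal safety collection would remain.

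**Conclusion.** The concern holds as a likely imbalance, not a demonstrated one. The text establishes that the arms have unequal opportunities for detection and that a reported adverse event removes a participant from the primary set; no legible section offsets either.

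The size cannot be known from the documents. About 3.6 versus 1.2-2.0 exclusions rests on assumed risk, assumed detection shares and an assumed 20 otherwise evaluable per arm, and choosing unequal detection guarantees unequal exclusions. It shows that the effect could amount to a couple of participants in an arm of 20, not that it will.

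A reader might infer that the efficacy result is biased against cefixime. The documents do not support a direction: the PP proportion can be too high, too low or unaffected. Only the adverse-event counts have an expected direction, since closer observation tends to make cefixime look worse. The point merits correction because the remedy is cheap.

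**What to change.** Extend the 2-week phone assessment to all remaining penicillin participants. Ask the same adverse-event questions in both arms at week 2 and at months 3 and 6, and record the contact at which each event was first reported.

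Where penicillin participants have already passed week 2 without the contact, do not let events found only at the cefixime arm's 2-week contact decide PP membership. State this rule before the arms are summarised. Report adverse events by arm in all treated participants, with the difference in collection stated.

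The cost is one call by existing staff per remaining penicillin participant and a short amendment. That is at most about 25 calls if 50 is the total enrolment, or 50 if it is per arm. Changing collection midway adds some heterogeneity. The gain shrinks if few participants remain to be enrolled: recruitment began in September 2018, the study was planned for 2 years, and the document is dated August 2020, although recruitment is described as ongoing. The PP rule and the reporting by arm remain useful even then.

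### No clear rule covers syphilis-active antibiotics taken after enrolment, and the visit question does not reach months 0-3 for per-protocol participants seen only at month 6

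*Combined protocol and SAP*

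**What the plan says.** All references are to the combined protocol and SAP.

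- **Collection.** Intervention description {11a} sets the schedule: "Study staff will follow up with all participants at 3, 6, and 12 months. In each follow up", and then "participants are asked questions regarding symptoms, antibiotic use in the past 3 months and" sexual partners over the same period. Plans for assessment and collection of outcomes {18a} lists antibiotic use as an item at each follow-up visit, with no look-back period. Relevant concomitant care {11d} makes a broader promise: concomitant "antibiotic use during the participation in the study duration of the trial will be recorded". It gives no method.
- **Analysis set.** Statistical methods {20a} makes PP the primary population. Besides meeting the eligibility criteria and completing treatment, members must "report no adverse events, returned for follow-up visits (3 and/or 6 months) and have an evaluable" RPR result. A month-3 visit is not required.
- **Endpoint.** Outcomes {12} counts a fall of at least 4-fold in RPR from baseline to month 3 or month 6 as success. It does not mention other antibiotics.
- **Eligibility.** Exclusion criterion 4 in {10} begins "Recent (within the past 7 days) or concomitant antimicrobial therapy with activity against" and continues "syphilis, namely azithromycin, doxycycline, ceftriaxone or other beta lactam antibiotics (e.g" amoxicillin). It does not say whether the concomitant part still applies once a participant is enrolled.

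**The concern.** The protocol itself names several antibiotics as active against syphilis and treats their use as a reason not to enrol. After enrolment it has no clear counterpart. A participant who takes one of them and then shows a 4-fold fall is, on the literal PP list and endpoint, a success for the assigned drug.

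The sites provide care and treatment for sexually transmitted infections, so such prescriptions are plausible. The trial is non-comparative and each arm's proportion stands alone, so a similar effect in the penicillin arm would not cancel an upward shift in the cefixime estimate.

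A rule added later could be applied only if use and dates had been captured throughout the primary window. For a participant whose first follow-up is at month 6, the described question does not do that.

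**Working it through.** **1. What the question covers.**

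| Visits attended in the primary window | Months covered by a 3-month look-back | Not reached | Can be in PP |
|---|---|---|---|
| 3 and 6 | 0-3 and 3-6 | none | yes |
| 3 only | 0-3 | none before the only RPR used | yes |
| 6 only | 3-6 | 0-3 | yes |

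The gap is confined to the last row. That row is inside the primary analysis, and a month-6 fall alone makes the participant a success.

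**2. What happens to use that is recorded.** Take a participant who attends both visits and reports doxycycline at month 2. {12} still counts a 4-fold fall at month 3 or 6. {20a} removes the participant only if criterion 4 is read as continuing after entry, which the text does not settle. So complete recording alone would not change the result. A rule is needed, and the rule needs the data.

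**3. The plan's own figures.** Sample size {14} assumes 40 evaluable participants and 90% response, which is 36/40. The exact (Clopper-Pearson) 95% interval is 0.763 to 0.972, matching the stated (0.76, 0.97). Enrolment is 40 / (1 - 0.20) = 50, as stated. Neither figure is in dispute.

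**4. Size of the unseen part.** The documents give neither rate, so both are assumptions:

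- m = share of PP participants seen at month 6 but not month 3: 10-20%.
- a = share taking a syphilis-active antibiotic in months 0-3: 10-20%.
- f = share of those who would otherwise have failed: 10%, from the plan's 90% response.

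Unseen exposure = m × a, from 0.10 × 0.10 = 1% to 0.20 × 0.20 = 4%. In 40 PP participants that is 0.4 to 1.6 people.

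Bias = m × a × f, from 1% × 0.10 = 0.1 point to 4% × 0.10 = 0.4 point. This takes every exposed would-be failure to be turned into a success, so it is an upper figure for these inputs.

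With wider assumptions (m 5-20%, a 5-30%), exposure is 40 × 0.05 × 0.05 = 0.1 to 40 × 0.20 × 0.30 = 2.4 people. The largest bias is 0.20 × 0.30 × 0.10 = 0.6 point. At 4% exposure the bias reaches 1 point only if f is 25% (0.04 × 0.25 = 0.01).

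**5. Size of the part that is recorded but has no rule.** Dropping m, one quarter of exposure gives at most a × f = 0.10 × 0.10 to 0.20 × 0.10, or 1 to 2 points on the same assumptions. These cases would be visible in the data. What is missing is an agreed way to handle them.

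**6. Effect of the proposed rule.** Starting from 36/40 = 90.0% (0.763-0.972), removing one exposed responder gives 35/39 = 89.7% (0.758-0.971). Removing two gives 34/38 = 89.5% (0.752-0.971).

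**The case against.** The strongest reply is that the information may well exist. {11d} commits to recording antibiotic use throughout participation, and {18a} lists it at every follow-up visit without a time limit. The form itself is not in the documents, so {11a} may only summarise its wording. Participants sign a release of clinical and laboratory data ({26b}), and visits are timed to routine appointments in the same clinics ({11c}). The cefixime arm also has a clinical "assessment or have a phone call assessment with the study team member 2 weeks following" enrolment.

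Much of this stands. A reader might infer that antibiotic use in months 0-3 goes unrecorded for these participants. The documents do not support that, given {11d}. They support only that the described question does not deliver what {11d} promises. The other routes do not close the gap as written: no section says the clinic record is used for antibiotic history, and the 2-week contact has no stated content and covers one arm only.

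A reader might also blame the look-back period for the wrong crediting. It is not the main cause, because recorded use is credited too.

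One can argue that criterion 4 already removes later users, since PP requires the eligibility criteria to be met and the criterion mentions concomitant therapy. That reading is possible, but the criterion gives no period for it. This is why the rule is unclear rather than plainly absent.

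Two further inferences fail. With about 20 PP participants per arm, one participant is 5 points, and it is tempting to quote that as the bias. But {14} does not say whether 40 is per arm, the assumed rates give 0.8 of a person at most in 20 (20 × 0.04), and most of those exposed would have responded anyway. The month-12 question also misses months 6-9, but these lie outside the primary window and no month-12 analysis is stated.

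**Conclusion.** The point holds as a gap in the analysis rules, with incomplete data capture as a second part. {20a} and {12} do not clearly say how post-enrolment use of a syphilis-active antibiotic is handled, so a response after such use can count for the assigned treatment in either arm. {11a} and {11d} must be reconciled, because a PP participant seen only at month 6 is not asked about months 0-3.

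The effect is likely to be small. On assumed rates of 10-20% for each input, 1-4% of PP participants have an exposure the question misses, and the bias from these is probably under 1 point. That rests on about 10% otherwise failing; a lower true response would raise it. Against an interval running from 0.76 to 0.97 this does not threaten the trial's conclusion. It is a cheap improvement, not a major flaw.

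**What to change.** 1. **Collection ({11a}, aligned with {11d}).** At every visit, ask about antibiotic use since enrolment or since the last completed study visit, with drug and date. When a visit was missed, check the answer against the clinic record that participants already release.
2. **Analysis ({20a}).** State that, for analysis only, a participant who takes an agent listed in exclusion criterion 4 after enrolment and before the qualifying RPR fall leaves the PP set. Except the assigned study treatment, since the criterion's beta-lactam wording would otherwise catch both study drugs. Say that the rule also covers participants who take such an agent in the primary window and never show the fall; otherwise it would remove successes and keep failures. Report the number removed by arm, and show each arm's proportion and exact interval with and without them.

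The cost is one phrase on an existing form and a short addition to the PP definition. The downsides are longer recall after a missed visit and possibly one fewer PP participant. Nothing about treatment or clinical care changes.
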